4.2.2 Restrictions

4.2.2.1 Restrictions regarding concomitant treatment

In principle, no concomitant therapy is allowed. All concomitant or rescue therapies will be recorded (including time of intake on study days) on the appropriate pages of the CRF.

4.2.2.2 Restrictions on diet and life style

While admitted to the trial site, the subjects are restricted from consuming any other foods or drinks than those provided by the staff. Standardised meals will be served at the time points described in the [Flow Chart](#). For the SRD, no food is allowed for at least 4 h after drug intake.

From 1 h before drug intake until lunch, fluid intake is restricted to the milk served with breakfast (FE part Treatment T, see [Table 4.1.4: 2](#)), the water administered with the drug, and an additional 240 mL of water served on Day 1 at 2 h and 4 h post-dose (mandatory for all subjects).

Alcoholic beverages, grapefruits, Seville oranges (sour or bitter oranges) and their juices, and dietary supplements and products including St. John's wort (*Hypericum perforatum*) are not permitted starting 7 days before the first administration of trial medication until after the last PK sample of each study period is collected.

Poppy-seed containing products should not be consumed starting 4 days before first trial drug administration until last PK sampling of the trial.

Smoking is not allowed during in-house confinement at the trial site.

Methylxanthine-containing drinks or foods (such as coffee, tea, cola, energy drinks, and chocolate) are not allowed from 4 h before until 4 h after each administration of trial medication.

Excessive physical activity (such as competitive sport) should be avoided starting 7 days before the first administration of trial medication until the end of trial examination.

4.3 TREATMENT COMPLIANCE

Compliance will be assured by administration of all trial medication in the study centre under supervision of the investigating physician or a designee. The measured plasma concentrations and/or urinary excretion will provide additional confirmation of compliance.

Subjects who are non-compliant (for instance, who do not appear for scheduled visits or violate trial restrictions) may be removed from the trial and the CRF will be completed accordingly (for further procedures, please see [Section 3.3.4.1](#)).

5. VARIABLES AND THEIR ASSESSMENT

5.1 EFFICACY - CLINICAL PHARMACOLOGY

5.1.1 Endpoints of efficacy

No efficacy endpoints will be evaluated in this trial.

5.1.2 Assessment of efficacy

Not applicable.

5.2 SAFETY

5.2.1 Endpoints of safety

Primary endpoint to assess safety and tolerability of BI 1358894 is the number [N (%)] of subjects with drug- related adverse event.

Further criteria of interest:

- AEs (including clinically relevant findings from the physical examination)
- Safety laboratory tests
- 12-lead ECG
- Continuous ECG monitoring
- Vital signs (blood pressure, pulse rate, respiratory rate) and Orthostatic tests (SRD part only)
- Visual analogue scale (Bond & Lader)

5.2.2 Assessment of adverse events

5.2.2.1 Definitions of adverse events

Adverse event

An adverse event (AE) is defined as any untoward medical occurrence in a patient or clinical investigation subject administered a medicinal product and which does not necessarily have to have a causal relationship with this treatment.

An AE can therefore be any unfavourable and unintended sign (including an abnormal laboratory finding), symptom, or disease temporally associated with the use of a medicinal product, whether or not considered related to the medicinal product.

Serious adverse event

A serious adverse event (SAE) is defined as any AE which fulfils at least one of the following criteria:

Proprietary confidential information © 2018 Boehringer Ingelheim International GmbH or one or more of its affiliated companies

- results in death,
- is life-threatening, which refers to an event in which the patient was at risk of death at the time of the event; it does not refer to an event that hypothetically might have caused death if more severe,
- requires inpatient hospitalisation or
- requires prolongation of existing hospitalisation,
- results in persistent or significant disability or incapacity, or
- is a congenital anomaly/birth defect, or
- is deemed serious for any other reason if it is an important medical event when based upon appropriate medical judgment which may jeopardise the patient and may require medical or surgical intervention to prevent one of the other outcomes listed in the above definitions.

Examples of such events are intensive treatment in an emergency room or at home for allergic bronchospasm, blood dyscrasias or convulsions that do not result in hospitalisation or development of dependency or abuse.

AEs considered ‘Always Serious’

Cancers of new histology and exacerbations of existing cancer must be classified as a serious event regardless of the duration between discontinuation of the drug and must be reported as described in [Section 5.2.2.2](#), subsections ‘AE collection’ and ‘AE reporting to sponsor and timelines’.

In accordance with the European Medicines Agency initiative on Important Medical Events, Boehringer Ingelheim has set up a list of further AEs, which by their nature, can always be considered to be ‘serious’ even though they may not have met the criteria of an SAE as defined above.

The latest list of ‘Always Serious AEs’ can be found in the eDC system. These events should always be reported as SAEs as described above.

Adverse events of special interest (AESIs)

The term AESI relates to any specific AE that has been identified at the project level as being of particular concern for prospective safety monitoring and safety assessment within this trial, e.g. the potential for AEs based on knowledge from other compounds in the same class. AESIs need to be reported to the sponsor’s Pharmacovigilance Department within the same timeframe that applies to SAEs, please see above.

The following are considered as AESIs in this trial:

- Hepatic injury, as defined by the following alterations of hepatic laboratory parameters:
 - o an elevation of AST and/or ALT ≥ 3 -fold ULN combined with an elevation of total bilirubin ≥ 2 -fold ULN measured in the same blood sample, and/or
 - o aminotransferase (ALT, and/or AST) elevations ≥ 10 fold ULN

These lab findings constitute a hepatic injury alert and the patients showing these lab abnormalities need to be followed up according to the 'DILI checklist' provided in the ISF. In case of clinical symptoms of hepatic injury (icterus, unexplained encephalopathy, unexplained coagulopathy, right upper quadrant abdominal pain, etc.) without lab results (ALT, AST, total bilirubin) available, the Investigator should make sure these parameters are analysed, if necessary in an unscheduled blood test. Should the results meet the criteria of hepatic injury alert, the procedures described in the DILI checklist should be followed.

Intensity of AEs

The intensity of the AE should be judged based on the following:

Mild: Awareness of sign(s) or symptom(s) that is/are easily tolerated

Moderate: Enough discomfort to cause interference with usual activity

Severe: Incapacitating or causing inability to work or to perform usual activities

Causal relationship of AEs

Medical judgment should be used to determine the relationship, considering all relevant factors, including pattern of reaction, temporal relationship, de-challenge or re-challenge, confounding factors such as concomitant medication, concomitant diseases and relevant history.

Arguments that may suggest that there is a reasonable possibility of a causal relationship could be:

- The event is consistent with the known pharmacology of the drug
- The event is known to be caused by or attributed to the drug class.
- A plausible time to onset of the event relative to the time of drug exposure.
- Evidence that the event is reproducible when the drug is re-introduced
- No medically sound alternative aetiologies that could explain the event (e.g. pre-existing or concomitant diseases, or co-medications).
- The event is typically drug-related and infrequent in the general population not exposed to drugs (e.g. Stevens-Johnson syndrome).
- An indication of dose-response (i.e. greater effect size if the dose is increased, smaller effect size if dose is diminished).

Arguments that may suggest that there is no reasonable possibility of a causal relationship could be:

- No plausible time to onset of the event relative to the time of drug exposure is evident (e.g. pre-treatment cases, diagnosis of cancer or chronic disease within days / weeks of drug administration; an allergic reaction weeks after discontinuation of the drug concerned)
- Continuation of the event despite the withdrawal of the medication, taking into account the pharmacological properties of the compound (e.g. after 5 half-lives). Of note, this criterion may not be applicable to events whose time course is prolonged despite removing the original trigger.

Proprietary confidential information © 2018 Boehringer Ingelheim International GmbH or one or more of its affiliated companies

- Additional arguments amongst those stated before, like alternative explanation (e.g. situations where other drugs or underlying diseases appear to provide a more likely explanation for the observed event than the drug concerned).
- Disappearance of the event even though the trial drug treatment continues or remains unchanged.

5.2.2.2 Adverse event collection and reporting

AEs collection

Upon enrolment into a trial, the subject's baseline condition is assessed (for instance, by documentation of medical history/concomitant diagnoses), and relevant changes from baseline are noted subsequently.

[figure not shown]
Subjects will be required to report spontaneously any AEs as well as the time of onset, end, and intensity of these events. In addition, each subject will be regularly assessed by the medical staff throughout the clinical trial and whenever the investigator deems necessary. As a minimum, subjects will be questioned for AEs (and concomitant therapies) at the time points indicated in the [Flow Chart](#). Assessment will be made using non-specific questions such as 'How do you feel?' Specific questions will be asked wherever necessary in order to more precisely describe an AE.

A careful written record of all AEs shall be kept by the investigator in charge of the trial. Records of AEs shall include data on the time of onset, end time, and intensity of the event as well as any treatment or action required for the event and its outcome.

The following must be collected and documented on the appropriate CRF(s) by the investigator:

- From signing the informed consent onwards until an individual subject's end of trial:
 - All AEs (serious and non-serious) and all AESIs.
 - The only exception to this rule are AEs (serious and non-serious) and AESIs in Phase I trials in healthy volunteers, when subjects discontinue from the trial due to screening failures prior to administration of any trial medication. In these cases, the subjects' data must be collected at trial site but will not be entered in the CRF or trial database and will not be reported in the CTR.
- After the individual subject's end of trial:
 - The investigator does not need to actively monitor the subject for AEs but should only report related SAEs and related AESIs of which the investigator may become aware of by any means of communication, e.g. phone call. Those AEs should, however, not be reported in the CRF.

Proprietary confidential information © 2018 Boehringer Ingelheim International GmbH or one or more of its affiliated companies

The REP for BI 1358894, when measurable drug levels or PD effects are still likely to be present after the last administration, is not known for this first-in-human trial. Therefore, all AEs reported until the end of trial examination (last per protocol contact) will be considered on treatment (please see [Section 7.3.3](#)).

AE reporting to sponsor and timelines

The Investigator must report SAEs, AESIs, and non-serious AEs which are relevant for the reported SAE or AESI, on the BI SAE form via fax immediately (within 24 hours of awareness) to the sponsor's unique entry point (country specific contact details will be provided in the ISF). The same timeline applies if follow-up information becomes available. In specific occasions the Investigator could inform the sponsor upfront via telephone. This does not replace the requirement to complete and fax the BI SAE form.

With receipt of any further information to these events, a follow-up SAE form has to be provided. For follow-up information the same rules and timeline apply as for initial information.

Information required

For each AE, the investigator should provide the information requested on the appropriate eCRF pages and the BI SAE form, if applicable. The investigator should determine the causal relationship to the trial medication.

The following should also be recorded as an (S)AE in the CRF and BI SAE form (if applicable):

- Worsening of the underlying disease or of other pre-existing conditions
- Changes in vital signs, ECG, physical examination and laboratory test results, if they are judged clinically relevant by the investigator.

If such abnormalities already pre-exist prior to trial inclusion they will be considered as baseline conditions and should be collected in the eCRF only.

All (S)AEs, including those persisting after individual subject's end of trial must be followed up until they have resolved, have been assessed as 'chronic' or 'stable', or no further information can be obtained.

5.2.3 Assessment of safety laboratory parameters

For the assessment of laboratory parameters, blood and urine samples will be collected by the trial site at the time points indicated in the [Flow Chart](#) after the subjects have fasted for at least 10 h. Overnight fasting is not required at the discretion of the investigator or designee for retests.

The parameters that will be determined are listed in [Tables 5.2.3: 1](#) and [5.2.3: 2](#). Reference ranges will be provided in the ISF (Section 10).

Manual differential white blood cell count or urine sediment examinations will only be performed if there is an abnormality in the automatic blood cell count and clinically relevant in the opinion of the investigator or in the urinalysis, respectively.

Proprietary confidential information © 2018 Boehringer Ingelheim International GmbH or one or more of its affiliated companies

Table 5.2.3: 1

Routine laboratory tests

Functional lab group	Test name
Haematology	Haematocrit Haemoglobin Red blood cell count (RBC) Reticulocyte count White blood cell count (WBC) Platelet count Erythrocyte Sedimentation Rate (ESR) Neutrophils, eosinophils, basophils, monocytes, lymphocytes
Automatic WBC differential (relative and absolute)	
Manual differential WBC (if automatic differential WBC is abnormal and clinically relevant in the opinion of the investigator)	Polymorphnuclear neutrophils (segs), band neutrophils (stabs), eosinophils, basophils, monocytes, lymphocytes
Coagulation	Activated partial thromboplastin time (aPTT) Prothrombin time (Quick's test and INR) Fibrinogen
Enzymes	Aspartate transaminase (AST/GOT) Alanine transaminase (ALT/GPT) Alkaline phosphatase (AP) Gamma-glutamyl transferase (GGT) Glutamate dehydrogenase (GLDH) Creatine kinase (CK) CK-MB, only if CK is elevated Lactate dehydrogenase (LDH) Lipase Amylase
Hormones ¹	Thyroid stimulating hormone (TSH) fT3, fT4
Substrates ¹	Plasma glucose Creatinine Total bilirubin Direct bilirubin Total protein Protein electrophoresis (only at screening examination) Albumin Alpha-1-Globulin Alpha-2-Globulin Beta-Globulin Gamma-Globulin C-Reactive Protein (CRP) Uric acid Total cholesterol Triglycerides
Electrolytes	Sodium Potassium Calcium

Table 5.2.3: 1 **Routine laboratory tests (cont).**

Functional lab group	Test name
Urinalysis ¹ (Stix)	Urine nitrite Urine protein Urine glucose Urine ketone Urobilinogen Urine bilirubin Urine erythrocytes Urine leukocytes Urine pH
Urine sediment ¹ (microscopic examination if erythrocytes, leukocytes nitrite or protein are abnormal in urine)	Only positive findings will be reported (for instance, the presence of sediment bacteria, casts in sediment, squamous epithelial cells, erythrocytes, leukocytes)

¹ Protein electrophoresis only at screening. Hormones only at screening and end of trial.

The tests listed in [Table 5.2.3: 2](#) are exclusionary laboratory tests which may be repeated as required. The results will not be entered in the CRF/database and will not be reported in the CTR. Except drug screening, it is planned to perform these tests during screening only. Drug screening will be performed at screening, after admission to the trial site (SRD part) and prior to each treatment period (FE part).

Table 5.2.3: 2 **Exclusionary laboratory tests**

Functional lab group	Test name
Drug screening (urine)	Amphetamine/MDA Barbiturates Benzodiazepine Cannabis Cocaine Methadone Methamphetamines/MDMA/XTC Opiates Phencyclidine Tricyclic antidepressants
Infectious serology (blood)	Hepatitis B surface antigen (qualitative) Hepatitis B core antibody (qualitative) Hepatitis C antibodies (qualitative) HIV-1 and HIV-2 antibody/p24-antigen (qualitative)

To encourage compliance with alcoholic restrictions, a breath alcohol test (Alcotest® 7410,) will be performed at screening and prior to each treatment period, and may be repeated at any time during the study at the discretion of an investigator or designee. The results will not be included in the CTR.

The laboratory tests listed in [Table 5.2.3: 1](#) and [5.2.3: 2](#) will be performed with the exception of the urinalysis stix and drug screening tests. These tests will be performed at the

Proprietary confidential information © 2018 Boehringer Ingelheim International GmbH or one or more of its affiliated companies

trial site using Combur9 Test, and
AccuSign® DOA 10 test ().

Laboratory data will be transmitted electronically from the laboratory to the trial site.

5.2.4 **Electrocardiogram**

5.2.4.1 12-lead resting ECG

Twelve-lead resting ECGs (I, II, III, aVR, aVL, aVF, V1 - V6) will be recorded using a computerised electrocardiograph (CardioSoft EKG System,) at the time points given in the [Flow Chart](#).

In order to achieve a stable heart rate at rest and to assure high quality recordings at comparable resting phases, all ECGs will be recorded for a 10-second duration after the subjects have rested for at least 5 minutes in a supine position. The site personnel will be instructed to assure a relaxed and quiet environment so that all subjects are at complete rest during the recordings. ECG assessment will always precede all other study procedures of the same time point (except blood drawing from an intravenous cannula which is already in place) to avoid impact of sampling on the ECG quality.

Electrode placement will be performed according to the method of Wilson, Goldberger and Einthoven modified by Mason and Likar (hips and shoulders instead of ankles and wrists). Precise electrode placement will be marked with an indelible mark on the skin to allow reproducible placement throughout the study.

Single rising dose part: Triple ECGs will be recorded (within 180 sec) at all-time points as specified in the respective [Flow Chart](#). At all remaining time points, single ECGs will be recorded.

Food effect part: Single ECGs will be recorded for all time points. However, the number of ECGs per time point may be increased to three ECGs based on preliminary ECG results obtained during the single rising dose part of the study.

All locally printed ECGs will be evaluated by the investigator or a designee..

ECGs may be repeated for quality reasons (like alternating current artefacts, muscle movements, electrode dislocation). For time points with triple ECGs, all three single ECGs will be repeated. For the repeats due to quality reasons, only the repeated ECG recordings will be sent to the central ECG lab, whereas the initially recorded ECGs will be discarded.

Additional (unscheduled) ECGs may be collected by the investigator for safety reasons. These ECGs are assigned to the prior scheduled time point. Unscheduled ECGs will not be included into the statistical analysis of interval lengths.

For the inclusion or exclusion (see [Section 3.3](#)) of a subject and for the assessment of cardiac safety during the study, the QT and QTcB values generated by the ECG machines or their manual corrections by the investigators will be used. In doubtful cases, ECGs may be sent upfront for centralised evaluation (see below). In this case, these centrally measured results would overrule any other results obtained.

Proprietary confidential information © 2018 Boehringer Ingelheim International GmbH or one or more of its affiliated companies

Abnormal findings will be reported as AEs (during the trial) or baseline conditions (at screening), if judged clinically relevant by the investigator. Any ECG abnormalities will be monitored carefully and, if necessary, the subject will be removed from the trial and will receive the appropriate medical treatment.

Assessed ECGs will comply with the ICH E14 guidance document and supplements [[R05-2311](#), [R13-0801](#), [R13-4095](#)] as well as the FDA requirements for annotated digital ECGs [[R09-4830](#)].

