ANOVA	Analysis of variance
AST	Aspartate amino transferase
AUC	Area under the curve
AUC_{0-∞}	Area under the concentration-time curve of the analyte in plasma over the time interval from 0 extrapolated to infinity
AUC_{0-tz}	Area under the concentration-time curve of the analyte in plasma over the time interval from 0 to the last quantifiable data point
β	Slope parameter associated with the power model used to evaluate dose proportionality
BA	Bioavailability
BI	Boehringer Ingelheim
BLQ	Below limit of quantification
BMI	Body mass index (weight divided by height squared)
BP	Blood pressure
BW	Body weight
BPD	borderline personality disorder
CA	Competent authority
CI	Confidence interval
C_{max}	Maximum measured concentration of the analyte in plasma
CNS	Central Nervous System
C_{pre,N}	Predose concentration of the analyte in plasma immediately before administration of the Nth dose after N-1 doses were administered
CRF	Case report form
CRO	Clinical Research Organization
CT	Concomitant Therapy

Proprietary confidential information © 2018 Boehringer Ingelheim International GmbH or one or more of its affiliated companies

CTP	Clinical trial protocol
CTR	Clinical trial report
CV	Arithmetic coefficient of variation
DILI	Drug induced liver injury
DRF	Dose Range Finding
ECG	Electrocardiogram
EDC	Electronic data capture
EDTA	Ethylenediaminetetraacetic acid
EOT	End of trial
FDA	Food and Drug Administration
FE	Food Effect

FIH	First in Human
GCP	Good Clinical Practice
gCV	Geometric coefficient of variation
gMean	Geometric mean
GMP	Good Manufacturing Practice
hERG	human ether-a-go-go related gene
HIV	Human Immunodeficiency Virus
ICH	International Conference of Harmonisation
IEC	Independent Ethics Committee
IRB	Institutional Review Board
ISF	Investigator site file
LVSP	left ventricular pressure parameters
MDD	major depressive disorder
MedDRA	Medical Dictionary for Regulatory Activities
MRD	Multiple rising dose

nM	Nanomolar
NOA	Not analysed
NOAEL	No observed adverse effect level
NOR	No valid result
NOS	No sample available
PD	Pharmacodynamic(s)
PK	Pharmacokinetic(s)
PKS	Pharmacokinetic set
PR	Pulse rate

Proprietary confidential information © 2018 Boehringer Ingelheim International GmbH or one or more of its affiliated companies

QD	Once Daily
QT	Time between start of the Q-wave and the end of the T-wave in an electrocardiogram
QTc	QT interval corrected for heart rate using the method of Fridericia (QTcF) or Bazett (QTcB)
R	Reference treatment
REP	Residual effect period

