2.3.2 Risks related to the intake of BI 1358894

2.3.2.1 Risks derived from observations in non-clinical studies

Rats and dogs were employed as the animal species for general toxicology investigations on BI 1358894, because in-vitro and in-vivo profiling supported the suitability of both species for nonclinical safety profiling of BI 1358894.

As summarized in [Section 1.2.3](#), potential risks observed in non-clinical studies are a long lasting decrease of blood pressure in rats, an increase in heart rate in rats and dogs, and signs of a short lasting episode of arterial/ perivascular inflammation in rats. All findings were observed within 5 days after start of treatment. The CV effects observed in rodents and non-rodents can be easily monitored in a Phase I study (CV effects). Perivascular/mesenteric inflammation induced by BI 1358894 occurred early after start of dosing and resolved despite continued treatment, indicating its transient character. The non-clinical safety data support clinical Phase I trials in non-childbearing humans with daily oral administration for up to 4 weeks.

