3.3.3 Exclusion criteria

Subjects will not be allowed to participate if any of the following general criteria apply:

1. Any finding in the medical examination (including BP, PR or ECG) is deviating from normal
2. Repeated measurement of systolic blood pressure outside the range of 90 to 140 mmHg, diastolic blood pressure outside the range of 50 to 90 mmHg, or pulse rate outside the range of 50 to 90 bpm

Proprietary confidential information © 2018 Boehringer Ingelheim International GmbH or one or more of its affiliated companies

3. C-Reactive Protein > ULN, erythrocyte sedimentation rate (ESR) \geq 15 millimeters/hour, liver and kidney parameter above ULN, other laboratory values outside the reference range the investigator considers to be of clinical relevance
4. Any evidence of a concomitant disease judged as clinically relevant by the investigator
5. Gastrointestinal, hepatic, renal, respiratory, cardiovascular, metabolic, immunological or hormonal disorders
6. Cholecystectomy and/or surgery of the gastrointestinal tract that could interfere with the pharmacokinetics of the trial medication (except appendectomy and simple hernia repair)
7. Diseases of the central nervous system (including but not limited to any kind of seizures or stroke), and other relevant neurological or psychiatric disorders
8. History of relevant orthostatic hypotension, fainting spells, or blackouts
9. Chronic or relevant acute infections
10. History of relevant allergy or hypersensitivity (including allergy to the trial medication or its excipients)
11. Use of drugs within 30 days prior to administration of trial medication if that might reasonably influence the results of the trial (incl. QT/QTc interval prolongation)
12. Participation in another trial where an investigational drug has been administered within 60 days prior to planned administration of trial medication, or current participation in another trial involving administration of investigational drug
13. Smoker (more than 10 cigarettes or 3 cigars or 3 pipes per day)
14. Inability to refrain from smoking on specified trial days
15. Alcohol abuse (consumption of more 30 g per day for males)
16. Drug abuse as per investigator judgment or positive drug screening
17. Blood donation of more than 100 mL within 30 days prior to administration of trial medication or intended donation during the trial

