18. Intention to perform excessive physical activities within one week prior to administration of trial medication or during the trial
19. Inability to comply with dietary regimen of trial site
20. A marked baseline prolongation of QT/QTc interval (such as QTc intervals that are repeatedly greater than 450 ms in males) or any other relevant ECG finding at screening
21. A history of additional risk factors for Torsades de Pointes (such as heart failure, hypokalemia, or family history of Long QT Syndrome)
22. Subject is assessed as unsuitable for inclusion by the investigator, for instance, because considered not able to understand and comply with study requirements, or has a condition that would not allow safe participation in the study

In addition, the following trial-specific exclusion criteria apply:

23. Any lifetime history of suicidal behaviour (i.e. actual attempt, interrupted attempt, aborted attempt, or preparatory acts or behaviour)
24. Any suicidal ideation of type 2 to 5 on the C-SSRS in the past 12 months (i.e. active suicidal thought, active suicidal thought with method, active suicidal thought with intent but without specific plan, or active suicidal thought with plan and intent)

For study restrictions, refer to [Section 4.2.2](#).

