3.3.4.2 Discontinuation of the trial by the sponsor

Boehringer Ingelheim reserves the right to discontinue the trial overall or at a particular trial site at any time for any of the following reasons:

1. New toxicological findings or serious adverse events invalidate the earlier positive benefit-risk-assessment. More specifically, the trial will be terminated if more than 50% of the subjects show drug-related and clinically relevant adverse events of moderate or severe intensity, or if at least one drug-related serious adverse event is reported.
2. The expected enrolment goals overall or at a particular trial site are not met
3. Violation of GCP, or the CTP, or the contract with BI by a trial site or investigator, disturbing the appropriate conduct of the trial
4. The sponsor decides to discontinue the further development of the investigational product.
5. Dose escalation will be stopped as soon as at least 2 subjects at one dose level on active drug showed relevant individual QT prolongation, i.e. a QTc increase of greater 60 ms from baseline in connection with absolute QT or QTc greater than 500 ms, which has been confirmed by a repeat ECG recording.
6. Dose escalation will be stopped if the estimated exposure is expected to exceed a C_{max} of 1960 nM or an AUC_{0-24h} of 26300 nM*h. Estimation will be done based on preliminary mean values of AUC_{0-24h} and C_{max} of preceding dose groups (see [Section 7.3.4](#)).
7. Dose escalation will be stopped, as soon as at least 2 subjects at one dose level showed a sustained decrease in systolic blood pressure of over ≥ 20 mmHg for at least 2 hours after drug administration compared to baseline (Day 1, predose) which will be measured after 15 min in supine position (to avoid false positive signals because of the required prolonged resting period after drug intake).

The investigator / the trial site will be reimbursed for reasonable expenses incurred in case of trial termination (except in case of the third reason).

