#### **Listing of individual data**

For all quantitative endpoints, listings of individual data will be shown in Appendix 16.2. For QTcB and RR only listings will be provided. Occurrences of notable findings will be flagged.

Comments regarding the ECGs will be listed.

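### Eligibility and on-study cardiac safety rest on raw QT and Bazett QTcB alone; computing QTcF beside QTcB would be a cheap, minor improvement

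*Protocol*

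**What the plan says.** Protocol 5.2.4.1 (12-lead resting ECG) sets one rule for deciding who may enter and for judging cardiac findings after dosing: "the QT and QTcB values generated by the ECG machines or their manual corrections by the investigators will be used". Where a reading is uncertain, an ECG may be sent for central evaluation, and the central result then overrides the local one.

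Three other places depend on this rule:

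- Exclusion criterion 20 (Protocol 3.3.3) gives its QT limit as an example, "such as QTc intervals that are repeatedly greater than 450 ms in males", without naming the correction.
- Stopping rule 5 (Protocol 3.3.4.2) needs at least two subjects on active drug at one dose level with a QTc rise of more than 60 ms, "in connection with absolute QT or QTc greater than 500 ms", confirmed by a repeat ECG. It does not name the correction either.
- The abbreviation list allows QTc to mean Fridericia or Bazett.

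Section 5.2.4.1 settles the matter as QTcB, so there is no contradiction. Exclusion criterion 2 keeps out men with a repeated "pulse rate outside the range of 50 to 90 bpm", which fixes the range of resting rates at entry. Protocol 2.3.2.1 names "an increase in heart rate in rats and dogs" among the potential risks. SAP 7.8.4 states: "For QTcB and RR only listings will be provided".

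**The concern.** Bazett and Fridericia divide QT by different powers of the RR interval, so the same ECG can fall on different sides of a limit depending on the formula. Two consequences matter here.

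- **Entry.** At slow resting rates that the protocol admits, QTcB is the more permissive of the two. A man can sit at the example limit on QTcB and above it on QTcF.
- **On study.** If the drug raises heart rate, QTcB can rise with no change in QTcF. A reader who sees only QT and QTcB cannot easily separate the rate effect from a repolarisation effect.

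What is at stake is the quality of individual ECG decisions, mainly in the 200 mg fed group. That is the last planned group, with 8 men, or 16 if the one optional extra group is used (72 − 64 = 8). Neither the primary endpoint analysis nor the sample size depends on it.

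**Working it through.** **Inputs.** Example limit 450 ms (exclusion 20); entry pulse range 50 to 90 bpm (exclusion 2); +60 ms and 500 ms (rule 5). Assumed, because the documents give no value: a starting QTcF of 400 ms, and a QT–RR exponent b between 0.25 and 0.50. The plan states no QTcB–QTcF figure, so there is none to reproduce. RR below is the RR interval, not the respiratory rate.

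**Formulae.** RR = 60/HR in seconds; QTcB = QT/RR^(1/2); QTcF = QT/RR^(1/3). Hence QTcF = QTcB × RR^(1/6).

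**1. Entry, with QTcB held at 450 ms**

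| Rate (bpm) | Calculation | QTcF (ms) |
|---|---|---|
| 50 | 450 × 1.2^(1/6) | 463.9 |
| 55 | 450 × (60/55)^(1/6) | 456.6 |
| 60 | 450 × 1 | 450.0 |
| 75 | 450 × 0.8^(1/6) | 433.6 |
| 90 | 450 × (2/3)^(1/6) | 420.6 |

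The span over 50 to 90 bpm is 463.9 − 420.6 = 43 ms, and over 55 to 75 bpm it is 23 ms. The permissive part is at most 14 ms (at 50 bpm), and 7 ms at 55 bpm. The raw QT of the man at 50 bpm would be 450 × 1.2^(1/2) = 493 ms.

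**2. The reverse, with QTcF held at 450 ms.** QTcB is 450 × 1.2^(−1/6) = 436.5 ms at 50 bpm and 450 × (2/3)^(−1/6) = 481.5 ms at 90 bpm, a span of 45 ms. The span is much the same either way, so it cannot rank the two scales.

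**3. Rate rise on study.** With QTcF constant at 400 ms, going from 60 to 90 bpm moves QTcB to 400 × 1.5^(1/6) = 428 ms, a shift of +28 ms. That is nearly half of the 60 ms in rule 5.

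**4. Which scale depends less on rate?** Let QT = 400 × RR^b with no drug effect on QT, and let the rate rise from 60 to 90 bpm (RR = 2/3). The QTcB shift is 400 × (2/3)^(b−1/2) − 400, and the QTcF shift is 400 × (2/3)^(b−1/3) − 400.

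| b | QTcB shift (ms) | QTcF shift (ms) |
|---|---|---|
| 0.25 | +43 | +14 |
| 0.33 | +28 | 0 |
| 0.40 | +17 | −11 |
| 0.50 | 0 | −26 |

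On the log scale the break-even is (1/2 + 1/3)/2 = 0.417. QTcF is the less rate-dependent below it, QTcB above it.

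**5. Rule 5 from rate alone.** Start at QTcF 400 ms and 60 bpm, with QTcF constant. A rise of 60 ms in QTcB needs 60 × (460/400)^6 = 139 bpm, and QTcB 500 ms needs 60 × (500/400)^6 = 229 bpm. Both parts must be met. A man starting at the 450 ms example limit would need 60 × (510/450)^6 = 127 bpm at supine rest.

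**6. Falling rate.** Assume QTcF 440 ms at 65 bpm, then a fall to 55 bpm. On QTcF the rule is met above 500 ms. Baseline QTcB is 440 × (65/60)^(1/6) = 445.9 ms, so on QTcB the rule is met above 505.9 ms, which is QTcF 505.9 × (60/55)^(1/6) = 513.3 ms. The window in which QTcB would miss a case is 13 ms.

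**The case against.** The case for leaving the text alone is substantial.

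- **Choice of scale.** Both corrections are named in the protocol, and the documents give no QT–RR exponent for these men. A preference for QTcF is therefore not established from the plan. This stands.
- **Direction of the named risk.** The nonclinical signal is a rise in heart rate, which inflates QTcB and so errs toward caution. Masking needs a falling rate and then opens only a narrow window. This stands too, although a false signal still costs a decision.
- **Safeguards.** Raw QT is used alongside QTcB. Exclusion 20 requires repeated exceedance, and exclusion 1 separately bars a man if "Any finding in the medical examination (including BP, PR or ECG) is deviating from normal". Rule 5 requires a confirming ECG in at least two men. ECGs are taken after supine rest, with triplicates in the SRD part, and doubtful cases may be read centrally. Together these limit the effect. They do not remove it, because whether a case looks doubtful is judged first on QT and QTcB.
- **SAP.** The sentence on listings appears in a section from which much has been removed in the public version. It may imply that other ECG variables are summarised. It is not evidence that QTcF is missing from the analysis, and nothing here relies on that. The same holds for the central evaluation text to which Protocol 5.2.4.1 points.
- **Wording.** Naming the correction in exclusion 20 and rule 5 only tidies the text, since 5.2.4.1 already governs both.

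**Conclusion.** The point holds as a cheap improvement of minor size. Against QTcF, QTcB is permissive by up to 14 ms at the slowest resting rate admitted. It mixes rate with QT when the rate rises: 28 ms for 60 to 90 bpm, assuming QTcF constant at 400 ms. Seeing both values is useful whichever scale proves less rate-dependent.

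A reader might infer three stronger things that the documents do not support:

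- **That the 43 ms span proves QTcF right and QTcB wrong.** The reverse calculation gives 45 ms. The answer depends on an exponent that the plan does not give, and QTcF is the less rate-dependent only below about 0.417.
- **That a faster heart rate alone would halt escalation.** With QTcF constant, the rates needed are 127 bpm or more at supine rest, confirmed, in two men on active drug. A smaller exponent lowers this: at b = 0.25 and a 450 ms start it is 60 × (510/450)^4 = 99 bpm. That is the corner of the assumed range, and the documents show no human heart-rate effect of that size. Rule 5 also has little left to stop, since no planned group follows 200 mg fed and added doses may not exceed the approved highest dose.
- **That the trial never looks at QTcF.** Too much ECG text is absent from the public documents to say so.

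**What to change.** In Protocol 5.2.4.1, add that QTcF is computed from the recorded QT and RR interval and used beside QTcB at screening and in the 12-lead ECG data of each safety review (Protocol 3.1). Where the two disagree about a limit, send the ECG to the central evaluation already provided for, and ask it to return QT, heart rate and both corrections. Name the correction in exclusion 20 and rule 5 when the text is next opened. The numeric limits are for the sponsor.

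An optional check uses data in hand. Fit log QT on log RR in the drug-free ECGs (screening, predose, placebo) of the earlier groups, planned as 7 × 8 + 2 × 12 = 80 men, and see whether b lies below 0.417.

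**Cost.** One calculation and no added procedure, with a few more flags, central readings or exclusions. If the eligibility or stopping rules themselves are changed, an amendment with ethics committee and authority approval is needed (Protocol 8.1). The last group would then enter under a slightly different ECG rule from earlier groups, whose placebo subjects are pooled with theirs (Protocol 7.3.3).
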